4.3.1. Inclusion Criteria

For a list of inclusion criteria, see the most recent version of the Protocol.

4.3.2. Exclusion Criteria

For a list of exclusion criteria, see the most recent version of the Protocol.

4.3.3. Reasons for Withdrawal

Subject Withdrawal

Subjects' parents/guardians may voluntarily withdraw their consent for study participation at any time and for any reason, without penalty.

A subject may withdraw or be withdrawn from the study for any of the following reasons:

- Withdrawal of consent
- Subject lost to follow-up
- Termination of the study
- Any new information becomes available that makes further participation unsafe.

Subjects who wish to withdraw from further study participation will be asked to continue to participate in follow-up visits. At the time of withdrawal, subjects will undergo an early termination visit, if they are not willing to participate in the remaining follow-up visits.

Discontinuation of Treatment

A subject may be discontinued from treatment and continue to be followed if any of individual halting rules (see Protocol) are met.

4.4. Treatments

4.4.1. Treatments Administered

All active and placebo study products will be orally administered via oral dosing syringe or dosing cup. For older children in whom a dosing cup is preferred, parents will be instructed to measure the drug in the oral dosing syringe prior to transferring to the dosing cup.

4.4.2. Method of Assigning Subjects to Treatment Groups (Randomization)

Per International Conference on Harmonisation (ICH) guideline E6: Good Clinical Practice (GCP), screening records will be kept at each participating site to document the reason why an individual was screened, but failed trial entry criteria. The reasons why individuals failed screening will be recorded on screening logs maintained by each site.

Once consented and upon entry of demographic data and confirmation of eligibility for this trial, the subject will be enrolled. Subjects will be assigned to either placebo or active study drug (the same antibiotic that they were prescribed for the first 5 days of treatment). After a subject is enrolled, they will be given a random treatment assignment of study product to either short course or standard course therapy. Randomization to short vs. standard course therapy will be at a 1:1 ratio (approximately 200 subjects per treatment group). Subjects will be stratified by age group <24 months vs. 24-71 months), type of initial antimicrobial therapy, and initial treatment in an ED or outpatient clinic/urgent care center.

Enrollment of subjects will be performed online using the electronic data capture (EDC) system provided by the Statistical and Data Coordinating Center (SDCC). The list of randomized treatment assignments will be prepared by statisticians at the SDCC. The list will be used to assign each volunteer a treatment code after the necessary data have been entered into the EDC

system. A designated individual at each site will be provided with a treatment key, which links the treatment code to the actual treatment assignment, which will be kept in a secure place.

Instructions for subject enrollment are included in the Manual of Procedures (MOP). Manual back-up randomization procedures are provided in the MOP for use in the event that the site temporarily loses access to the Internet or the online enrollment system is unavailable.

4.4.3. Blinding

This is a double-blind clinical trial. The study subjects and their parents/guardians, investigators, and study team staff will remain blinded to study treatment assignment throughout the study. The subjects and their families, investigators, and study team staff will not be blinded to which of the three antibiotics (amoxicillin, amoxicillin-clavulanate, cefdinir) the subject was initially prescribed.

The study products and placebo will be prepared by the unblinded site Research Pharmacist. Only the pharmacy staff will be aware of the study product bottle assignments. For subjects randomized to standard course therapy, the pharmacy will provide the same medication prescribed initially. For subjects randomized to short course therapy, the pharmacy will provide a placebo that resembles the appearance (color and texture), flavor, and consistency of the active study product. All study products will be packaged with an identical appearance. Additional details regarding dispensing procedures will be included in the protocol-specific MOP.

The study product will be labeled with a numerical code that masks site investigators, site staff, parent(s)/guardian(s) and children to the formulation. The unblinded site Research Pharmacist will be the only person to perform the unmasking if needed. Additional details regarding labeling procedures will be included in the protocol-specific MOP.

During the consenting process it will be explained to the parents of any potential subjects that the study product (treatment or placebo) that will be provided for administration after Day 5, may or may not taste exactly the same as the originally prescribed medication, and that the look and smell may be slightly different because it might be supplied by a different manufacturer than that of the initially prescribed antibiotic. Parents will also be instructed that the amount or frequency of the prescribed study product has been made uniform across all study groups; therefore, the amount/frequency may be different than originally prescribed by their provider (e.g., receipt of once daily cefdinir is not excluded, but upon study entry, those subjects will receive either twice daily cefdinir or placebo).

4.5. Study Variables

The primary variables of interest in this study are the DOOR, ordinal clinical response, resolution of symptoms, adequate clinical response, and solicited events, as defined in Section 3.3.

As the safety profile of amoxicillin, amoxicillin-clavulanate, and cefdinir are well established, and this trial is not powered to detect new, unknown safety signals, there will be no unsolicited event collection during this study and only protocol-defined SAEs and Suspected Unexpected Serious Adverse Reactions (SUSARs) will be collected.

For a complete list of SAEs that will be collected, regardless of the relationship to the study drug, see the Protocol. SAEs will be graded for severity and assessed for relationship to study product.

See the Protocol for the schedule of events for this study.

Severity of Event: SAEs will be assessed by a licensed study physician listed on the Form FDA 1572 as the site principal investigator or appropriate sub-investigator using a protocol-defined grading system. For events not included in the protocol-defined grading system, the following guidelines will be used to quantify severity:

- Mild (Grade 1): Events require minimal or no treatment and do not interfere with the subject's daily activities.
- Moderate (Grade 2): Events result in a low level of inconvenience or concern with therapeutic measures. Moderate events may cause some interference with functioning and daily activities.
- Severe (Grade 3): Events interrupt the subject's usual daily activities and may require systemic drug therapy or other treatment. Severe events are usually incapacitating.

Relationship to Study Product: The study physician's assessment of an SAE's relationship to study product is part of the documentation process, but it is not a factor in determining what is or is not reported in this study. If there is any doubt as to whether a clinical observation is an SAE, the event should be reported. The relationship to study product must be assessed for SAEs using the terms: related or not related. In a clinical trial, the study product must always be suspect. To help assess, the following guidelines are used:

- Related – There is a reasonable possibility that the study product caused the adverse event. Reasonable possibility means that there is evidence to suggest a causal relationship between the study product and the adverse event.
- Not Related – There is not a reasonable possibility that the administration of the study product caused the event.

All SAEs will be:

- Assessed for severity and causal relationship by a physician listed on the Form FDA 1572 as the principal investigator (PI) or sub-investigator.
- Recorded on the appropriate SAE report form.
- Followed through resolution by a study physician.
- Reviewed by the safety monitor, the DSMB (periodic review unless associated), DMID Medical Monitor, and the local IRB.

Death, life-threatening events, hospitalization or prolongation of existing hospitalization, and other important medical events are part of the efficacy endpoints of this trial and will not be reported or collected as SAEs, unless meeting the SAE reporting criteria included in the Protocol.

Any AE that meets a protocol-defined serious criterion must be submitted immediately (within 24 hours of site awareness) on an SAE form to the DMID Pharmacovigilance Group.

In addition to the SAE form, selected SAE data fields must also be entered into the EDC web-based data entry system. Refer to the Manual of Procedures for details regarding this procedure. Timelines for submission of an SAE form are as follows:

- All non-accidental deaths and life-threatening events, regardless of relationship, will be recorded on the SAE form and sent by fax within 24 hours of site awareness of the death or event.
- All other SAEs, regardless of relationship, will be reported via fax by the site within 24 hours of becoming aware of the event.

Other supporting documentation of the event may be requested by the pharmacovigilance contractor and should be provided as soon as possible.

All SAEs will be followed until satisfactory resolution or until the PI or sub-investigator deems the event to be chronic or the subject to be stable.

5. SAMPLE SIZE CONSIDERATIONS

The null hypothesis corresponding to the primary analysis of this study is:

H0: The sum of the probability that a subject assigned to the 5-day arm will have a higher DOOR than if assigned to the 10-day arm plus one-half the probability of equal DOORs is 50% (i.e., no difference in DOOR).

The primary study sample size is based on a superiority test of the null hypothesis above, under an assumed alternative hypothesis that the sum of the probability that a subject assigned to the 5-day arm will have a higher DOOR than if assigned to the 10-day arm plus one-half the probability of equal DOORs is 60% (p=60%).

A sample size of 360 (180 per arm) provides 90% power using a 2-sided alpha=0.05 with a Wilcoxon Mann-Whitney U test (see calculation below). If p=65% or 70%, then a total sample size of 160 (80 per arm) or 90 (45 per arm), respectively, would be required. The sample size is inflated by ~10% based on an estimate from a similar study, in order to account for loss to follow-up resulting in a total sample size of 400 (200/arm).

Sample size calculations were based on the formula below (Noether 1987):

$$N = \frac{(z_{\alpha} + z_{\beta})^2}{12c(1-c)\left(p'' - \frac{1}{2}\right)^2}$$

$$z_{\alpha} = \Phi^{-1}(0.975); z_{\beta} = \Phi^{-1}(0.90); (90\% \text{ power for two-sided test with } 5\% \text{ Type I error})$$

$$c = 0.5 \text{ (equal allocation to treatment arms)}$$

$$p'' = 0.6 \text{ (Pr(Higher DOOR) under alternative hypothesis)}$$

Note that the primary analysis statistical methods use the ITT analysis population and will account for missing data with multiple imputation. The exact analysis method was not used for the power calculation because it would require an excessive amount of assumptions about the nature and patterns of missing data in the final dataset and relationships of components of the imputation model to the primary outcome. Instead, a complete case analysis assuming 90% evaluable for analysis was used to obtain approximately 90% power in the actual analysis.

6. GENERAL STATISTICAL CONSIDERATIONS

6.1. General Principles

All continuous variables will be summarized using the following descriptive statistics: n (non-missing sample size), mean, standard deviation, median, maximum and minimum. The frequency and percentages (based on the non-missing sample size) of observed levels will be reported for all categorical measures. In general, all data will be listed, sorted by site, treatment and subject, and when appropriate by visit number within subject. All summary tables will be structured with a column for each treatment and will be annotated with the total population size relevant to that table/treatment, including any missing observations.

6.2. Timing of Analyses

One interim analysis will be performed and reported to the data and safety monitoring board (DSMB) after approximately 30% of the targeted subjects have completed the study. The interim analysis will inform DSMB decisions regarding stopping early for efficacy, futility, or safety.

The final analysis will be performed after database lock. Specific tables and figures may be released after DMID approval prior to CSR completion.

6.3. Analysis Populations

The primary analysis will be performed using the intention-to-treat (ITT) cohort. Other analyses, as specified below, may use complete case (CC) or according-to-protocol (ATP) cohorts.

Analyses of the ITT cohort will include imputation for missing data, while analyses of CC and ATP cohorts will not contain missing data by design, because they are required to have sufficient data to define unambiguously the Outcome Assessment Visit #1 DOOR or Outcome Assessment Visit #2 DOOR.

Reasons for exclusion from each analysis population are summarized in [Table 5](#) and shown by subject in [Listing 4](#). Excluded subjects might satisfy multiple criteria justifying their exclusion, but will have only one reason indicated in [Table 5](#) and [Listing 4](#). The reason indicated will be determined by the following rules.

ITT Exclusions

- Subject became ineligible before taking study product.

CC-V1 Exclusions

- Subject not treated with study product
- Not excluded for any reason above, but early termination before Outcome Assessment Visit #1 (subjects will be tabulated by reason for termination)
- Not excluded for any reason above, missing DOOR at Outcome Assessment Visit #1 component: Adequate Clinical Response
- Not excluded for any reason above, missing DOOR at Outcome Assessment Visit #1 component: Resolution of Symptoms

- Not excluded for any reason above, missing DOOR at Outcome Assessment Visit #1 component: Solicited Event Severity Days 1-5
- Not excluded for any reason above, missing DOOR at Outcome Assessment Visit #1 component: Number of Days of Antibiotic Use

CC-V2 Exclusions

- Subject not treated with study product
- Not excluded for any reason above, but early termination before Outcome Assessment Visit #2 (subjects will be tabulated by reason for termination)
- Not excluded for any reason above, missing DOOR at Outcome Assessment Visit #2 component: Adequate Clinical Response
- Not excluded for any reason above, missing DOOR at Outcome Assessment Visit #2 component: Resolution of Symptoms
- Not excluded for any reason above, missing DOOR at Outcome Assessment Visit #2 component: Solicited Event Severity Days 1-18
- Not excluded for any reason above, missing DOOR at Outcome Assessment Visit #2 component: Number of Days of Antibiotic Use

ATP-V1 Exclusion Reasons

- The subject was excluded from CC-V1 cohort
- Not excluded for any reason above, subject did not receive at least one dose of study product each day from Day 1 to Day 5
- Not excluded for any reason above, major protocol deviation (see Section 6.3.3; subjects will be tabulated by type of protocol deviation)
- Outcome Assessment Visit #1 occurred out of the protocol defined window of Day 6-10
- Outcome Assessment Visit #1 did not occur as an in-person visit

ATP-V2 Exclusion Reasons

- The subject was excluded from CC-V2 cohort
- Not excluded for any reason above, subject did not receive at least one dose of study product each day from Day 1 to Day 5
- Not excluded for any reason above, major protocol deviation (see Section 6.3.3, subjects will be tabulated by type of protocol deviation)
- Outcome Assessment Visit #2 occurred out of the protocol defined window of Day 19-25
- Outcome Assessment Visit #2 did not occur as an in-person visit

6.3.1. Intention-to-Treat Analysis (ITT) Cohort

The ITT cohort will include all randomized subjects that were still eligible on Day 1 of the study. The analyses on the ITT cohort will be performed per randomized treatment assignment.

Randomized subjects who became ineligible before Day 1 of the study and did not take any study product will be excluded from ITT. Subjects randomized but not treated for other reasons other than ineligibility will be analyzed in the ITT cohort, but will have adequate clinical response and its components treated as missing. Therefore, in ITT analyses, OCR and DOOR will be missing and will need to be imputed for subjects that were not treated. If data (solicited events, cough, etc.) are collected post-randomization for a subject that was not treated, that data will be used in the ITT analysis to assist in imputing the OCR and DOOR.

6.3.2. Complete Case (CC) Cohorts

Subjects in a CC analysis are analyzed as randomized but excluded from analysis if missing data prevents assigning an unambiguous value to the DOOR endpoint or if the subject has not received at least one dose of study product. The CC-V1 cohort will consist of all subjects with sufficient data to define unambiguously the Outcome Assessment Visit #1 DOOR. The CC-V2 cohort will consist of all subjects with sufficient data to define unambiguously the Outcome Assessment Visit #2 DOOR.

6.3.3. According-to-Protocol (ATP) Cohorts

Subjects in an ATP analysis require no major protocol deviations, and recorded receipt of at least one dose of study product each day from Day 1 to Day 5. What constitutes a major protocol deviation will be assessed on a case-by-case basis by a DMID/VTEU/ARLG committee prior to any member of the committee being unblinded to treatment assignments. Subjects in an ATP analysis will be analyzed as treated. The ATP-V1 cohort will restrict subjects to those in CC-V1 that furthermore meet the ATP requirements. The ATP-V2 cohort will restrict subjects to those in CC-V2 that furthermore meet the ATP requirements.

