6.3 Modification of Study Intervention/Investigational Product for a Participant

No modifications of study product are planned at this time. If a subject experiences any individual halting rule, as defined in Section 9.5.2, they will be taken off of the study drug.

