9.5.2 Individual Halting Rules (Termination of Study Product Administration)

Study product administration may be discontinued if any of the following criteria are met:

- Any clinical adverse event (AE), intercurrent illness, or other medical condition occurs that, in the opinion of the investigator, continued receipt of study product would not be in the best interest of the subject;
- New onset of illness or condition that meets exclusion criteria
- Inadequate clinical response that requires off-study antimicrobial therapy.
 - Subjects who require off-study antimicrobial therapy will be defined as having an inadequate clinical response.

Subjects may stop study drug treatment at any time of their own volition or at the advice of their treating provider or the study investigators. Subjects who stop study product for any reason will be regarded as having withdrawn from treatment but not as having withdrawn from the study (i.e, subjects will be asked to continue to participate in follow-up visits). All subjects with an inadequate clinical response will be referred to a non-study healthcare provider for evaluation and possible treatment outside of the clinical study.

At the time of withdrawal, subjects will undergo an early termination visit if they are not willing to participate in the remaining follow-up visits

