11.4 Final Analysis Plan

The primary analysis of the primary endpoint will be performed according to an intention-to-treat (ITT) approach and include all randomized subjects. As (secondary) sensitivity analyses of the primary endpoint, complete case analyses using the CC-V1 / ATP-V1 cohorts (defined below) and a worst case analysis using the ITT cohort of the primary endpoint will be performed. Additional analyses may be performed and are described in detail in the Statistical Analysis Plan.

Intention-to-Treat Cohort: All randomized participants, analyzed as randomized. Subjects that have not received at least one dose of study product will have adequate clinical response and its sub-components treated as missing.

Complete Case Cohorts (CC): Subjects in a CC analysis are analyzed as randomized, but excluded from analysis if missing data prevents assigning an unambiguous value to the DOOR endpoint or if the subject has not received at least one dose of study product. The CC-V1 cohort will consist of all subjects with sufficient data to define unambiguously the Visit #1 DOOR. The CC-V2 cohort will consist of all subjects with sufficient data to define unambiguously the Visit #2 DOOR.

According-to-Protocol Cohorts (ATP): Subjects in an ATP analysis require at least one dose of study product each day from Day 1 to Day 5 and furthermore subjects will be excluded from analysis if missing data prevents assigning an unambiguous value to the DOOR endpoint. The ATP-V1 cohort will restrict subjects to those with sufficient data to define unambiguously the Visit #1 DOOR. The ATP-V2 cohort will restrict subjects to those with sufficient data to define unambiguously the Visit #2 DOOR.

Details of what constitutes sufficient data to assign an unambiguous value to DOOR will be specified in the statistical analysis plan.

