3.3. Study Definitions and Derived Variables

DOOR is defined as follows:

1. Each subject is evaluated according to the ordinal composite outcome (See [Table 1](#)) and assigned an outcome rank ranging from 1-8. The ordinal outcome is referred to elsewhere in the SAP as the ordinal clinical response (OCR).
2. Desirability of Outcome Ranking (DOOR) is then assigned according to two rules:
 - i. When comparing two subjects with different ordinal responses, the subject with a better ordinal response receives a higher rank.
 - ii. When comparing two subjects with identical ordinal responses, the subject with fewer days of antibiotic use receives a higher rank.

The ordinal composite outcome involves an assessment of whether the subject has an adequate clinical response and whether they have experienced any solicited events as defined in [Table 1](#).

Table 1: Ordinal Outcome

	Adequate clinical response¹ (Assessed at Outcome Assessment Visits #1 and #2)	Solicited events³ (Assessed at Outcome Assessment Visits #1 and #2)
1	Yes, with resolution of symptoms ²	None
2	Yes, with resolution of symptoms ²	Mild (Grade 1)
3	Yes, with resolution of symptoms ²	Moderate (Grade 2)
4	Yes, with resolution of symptoms ²	Severe (Grade 3)
5	Yes, with persistent symptoms of fever, tachypnea, or cough	None or any grade
6	No, with ED/clinic visit but no hospitalization	None or any grade
7	No, with hospitalization	None or any grade
8	Death from any cause	

¹ Adequate clinical response is defined as the absence of a medically attended visit to an ED or outpatient clinic or hospitalization for persistent or worsening pneumonia that occurs after randomization and receipt of at least one dose of study drug.

- Persistent or worsening pneumonia is defined as receipt of a non-study systemic antibiotic for pneumonia or treatment for a complication of pneumonia, including drainage of pleural fluid, placement of a chest tube, video assisted thoracoscopic surgery, or thoracotomy procedures.

- Note: Receipt of a non-study antibiotic will not be regarded as satisfying this definition if it is related to a new diagnosis that is unrelated to the prior diagnosis of pneumonia.

² Resolution of symptoms is defined as the absence of all of the following:

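### The ATP cohorts require a study dose on every day from Day 1 to Day 5, with no exception for product stopped under protocol 9.5.2, so some early failures leave the cohort because of their outcome (minor)

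*SAP*

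**What the plan says.** The dosing rule appears three times.

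- SAP 6.3.3 requires "recorded receipt of at least one dose of study product each day from Day 1 to Day 5".
- SAP 6.3 lists as an exclusion reason, for both ATP-V1 and ATP-V2, that the "subject did not receive at least one dose of study product each day from Day 1 to Day 5".
- Protocol 11.4: "Subjects in an ATP analysis require at least one dose of study product each day from Day 1 to Day 5".

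None of these provides for study product stopped under the protocol. The blinded committee in SAP 6.3.3 rules on major protocol deviations. The dosing line is a separate reason, so the committee offers no way back in.

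The protocol does provide for stopping. Section 9.5.2 opens: "Study product administration may be discontinued if any of the following criteria are met". Its list includes "Inadequate clinical response that requires off-study antimicrobial therapy". Section 6.3 is worded more strongly: "If a subject experiences any individual halting rule, as defined in Section 9.5.2, they will be taken off of the study drug". Children who stop remain in follow-up (protocol 5.3.4 and 9.5.2), and those with an inadequate response before the first outcome visit are asked to attend both visits (protocol section 4).

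A pneumonia failure on Days 1-5 sets OCR 6, or 7 with hospitalization (SAP 6.5.1 and 6.5.5).

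**The concern.** The event that permits stopping is, for pneumonia failures, also the event that gives the worst ranks short of death. A child who fails on Days 1-4, is stopped and attends the first outcome visit has followed the protocol, has a known OCR and can be in CC-V1. The missing later doses still remove that child from ATP-V1 and ATP-V2. Membership then depends on the endpoint. If early failures differ by arm, the ATP estimate moves in favour of the arm with more of them.

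The same rule removes a child stopped for a severe reaction (OCR 4) and a child who dies before a Day 5 dose (OCR 8).

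ATP results are used in three places: as one of three sensitivity analyses of DOOR (SAP 8.2.2), in the DSMB report if the interim boundary is crossed (SAP 6.6), and in Tables 36 and 38, which print a Yes/No against 0.40 for OCR.

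**Working it through.** **Plan figures.** The plan gives no figure for the ATP rule. The 180 per arm used here comes from SAP section 5. Its formula gives (1.960 + 1.282)² / (12 × 0.25 × 0.10²) = 351, against 360 stated, so the planned size is consistent.

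**Who is removed.** Removed: failures on Days 1-4 whose product is stopped. Kept: failures on Day 5 after that day's dose, failures on Days 6-18 in ATP-V2, and failing children who keep taking study product.

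**Failure rate.** The only observation in the documents is no treatment failure in the 5-day or 10-day group of a cited trial described as underpowered (protocol 2.2, SAP 4.2). All rates below are assumptions, written short/standard.

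**Formula.** If the arms differ only in failure rate f, Pr(better OCR in short course) + 0.5 Pr(tie) = 0.5 − (fS − fT)/2. Removing a share s of failures gives f′ = f(1 − s)/(1 − sf). With failures even over the window and all Days 1-4 failures stopped, s = 4/5 for ATP-V1 and 4/18 for ATP-V2.

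Example at 5%/1%, ATP-V1: fS′ = 0.05 × 0.2 / 0.96 = 0.0104; fT′ = 0.01 × 0.2 / 0.992 = 0.0020; probability = 0.5 − 0.0084/2 = 0.496.

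| Failure, short/standard | All children | ATP-V1 | Removed of 180 per arm (180 × 0.8 × f) |
|---|---|---|---|
| 2%/1% | 0.495 | 0.499 | 2.9 vs 1.4 |
| 5%/1% | 0.480 | 0.496 | 7.2 vs 1.4 |
| 10%/2% | 0.460 | 0.491 | 14.4 vs 2.9 |

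Variations at 5%/1%:

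- ATP-V2: 0.480 becomes 0.484.
- If half of Days 1-4 failures are stopped (s = 0.4), ATP-V1 is 0.488; if a quarter (s = 0.2), 0.484.
- If only 75% of failures attend, CC is 0.485 and current ATP 0.497.
- DOOR goes from 0.607-0.725 to 0.629-0.753. This assumes 0 against 5 antibiotic days within OCR 1-5, even ties in OCR 6-7, and three assumed OCR 1-5 distributions for non-failures (55/22/9/2/12, 70/12/5/1/12 and 40/25/15/5/15%).

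**Verdict against 0.40.** Lower limits use the same three distributions, failures split 90/10 between OCR 6 and 7, and the Mann-Whitney variance with the tie term divided by N(N − 1).

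| Failure | All children, lower limit | ATP-V1, lower limit |
|---|---|---|
| 10%/0% | 0.393-0.400 (just below 0.40) | 0.431-0.439 |
| 11%/1% | 0.393-0.3996 | 0.430-0.439 |
| 12%/2% | 0.392-0.399 | 0.430-0.438 |

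At 10%/2%, an 8-point excess, both limits stay above 0.40. The halting rule in protocol 9.5.1 (more than 5% failing within 3 days) would not by itself exclude these rates: at 12%/2%, pooled 3-day failure is (12% + 2%)/2 × 3/5 = 4.2%.

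**Reaction stops added.** These are placed at OCR 4, all on Days 1-4, all attending. An exception for any 9.5.2 criterion returns the all-children value.

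| Failures; reaction stops | All children | Current ATP | Exception for failures only |
|---|---|---|---|
| 2%/1%; 1%/3% | 0.501-0.502 | 0.499 | 0.495 |
| 3%/1%; 1%/3% | 0.496-0.497 | 0.498 | 0.490 |
| 5%/1%; 1%/3% | 0.486-0.487 | 0.496 | 0.480 |
| 3%/1%; 3%/1% | 0.482-0.483 | 0.498 | 0.490 |

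An exception for failure stops alone would be one-sided.

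**The case against.** An ATP cohort is defined by adherence after randomization, so some selection of this kind is expected. ITT is primary, and the excluded failures are visible elsewhere. Tables 26 and 28 give failure by arm in the CC cohorts. Table 57 gives pneumonia visits, antibiotics and hospitalizations. The DSMB receives a risk-difference plot of adequate response and its components for every treated child who completed the first outcome visit, whatever the interim p-value. If the boundary is crossed, CC and worst-case results accompany ATP. Enrolment requires clinical improvement and the cited trial saw no failures, so 5%/1% within five days may be high. At 2%/1% the shift is 0.004, against a 95% half-width of 0.049-0.057.

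All of this stands, and it sets the weight. It does not remove the defect: an adherence cohort need not treat a stop that the protocol allows as non-adherence.

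A reader might infer more than the documents support:

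- That all failures are removed. Several groups stay in, as listed in the working.
- That the rule always favours short course. Removing reaction stops can push the other way, and the net direction depends on rates not given.
- That failures are hidden from the DSMB or from the final report. They are not.
- That the Yes/No in Tables 36 and 38 is unsafe at plausible rates. It takes an excess of about 10 points.

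**Conclusion.** The concern holds as a minor point. The text of SAP 6.3, SAP 6.3.3 and protocol 11.4 makes ATP membership depend on the outcome for children stopped under 9.5.2, whatever the failure rate. The primary analysis is untouched.

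The numerical effect is small at low failure rates (0.004 at 2%/1%) and moderate at 5%/1% (0.016 in ATP-V1, 0.004 in ATP-V2). These figures are upper cases for their rates, because they assume that every Days 1-4 failure is stopped; protocol 6.3 and 9.5.2 differ on whether that would happen. They also assume failures spread evenly over the window, full attendance, and arms that are otherwise alike.

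Agreement between ATP and the primary result should therefore not be read as reassurance about early failures.

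**What to change.** In SAP 6.3 and 6.3.3, before unblinding, state that the dosing requirement is met by at least one dose each day from Day 1 to Day 5, or to the day study product was stopped for a documented 9.5.2 criterion (whoever initiated the stop), or to death. Keep these children with their observed OCR. Family-choice stops with no listed 9.5.2 reason, and unexplained missed doses, stay excluded.

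For deaths this sentence is not enough. The early-termination lines of the CC lists, and the out-of-window and not-in-person lines of the ATP lists, must also be waived. Otherwise drop the death part.

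Split the missed-dosing row of Table 5 by reason and arm. Reasons for stopping are already planned (SAP 7.1, Listing 1), so this is mainly presentation.

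Reconcile two pairs of passages. Protocol 6.3 and 9.5.2 differ on whether product will or may be stopped, and this decides how many children are affected. Protocol 9.5.2 also says "Subjects who require off-study antimicrobial therapy will be defined as having an inadequate clinical response", while the SAP Table 1 note says "Receipt of a non-study antibiotic will not be regarded as satisfying this definition if it is related to a new diagnosis" unrelated to the pneumonia. Under the exception above, the second conflict affects only the reason label in Table 5.

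Cost: a sentence in two SAP sections, sub-rows in one table, and the difference from protocol 11.4 recorded by amendment (through the IRB, protocol 14.2) or in the CSR, as the SAP Preface allows. ATP also moves closer to CC and adds less as a separate analysis. It is not always nearer the all-children value: with 75% of failures attending, 3%/1% failures and 1%/3% reaction stops, all children give 0.496-0.497, the revised ATP 0.499-0.500 and the current ATP 0.498.

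If no change to the cohort is wanted, keep it, report the Table 5 split and state the limitation.
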